### **7.2 Secondary Endpoints**

1. Tissue volume imaged with curved paddle is greater than that for standard paddle
2. Image quality when using the curved paddle is non-inferior to the image quality of the standard paddle

This study will investigate and measure the potential reduction in pain to the breast with the curved paddle when compressing breast tissue to tautness as compared to the standard of care paddle compressing breast tissue to tautness. The potential improvement in the comfort of a mammographic exam for patients while looking at ease in positioning for technologists, without a loss in image quality, would offer a less painful, high quality procedure, which may potentially increase mammography compliance rates.

## **8. STUDY OVERVIEW**

The proposed study is designed to evaluate the following parameters and how they may affect pain during a mammogram: breast thickness, breast spread and compression force with the investigational curved paddle using compression force to achieve tautness for imaging. (The current standard for mammographic compression is to compress to tautness which may be determined by observing or touching the skin surface. The same parameters will be captured for the standard paddle at tautness. (Tautness compression captured as a function of force may differ between the two paddles based on the curved design of the investigational paddle versus the flat design of the standard paddle.)

## **9. STUDY DESIGN**

The study will be conducted in the United States at up to 5 centers. The study will enroll up to 650 subjects. The number of subjects was chosen to allow evaluation of screening and diagnostic patients with a variety of breast densities (fatty, scattered densities, heterogeneously dense or extremely dense) and women with a range of breasts sizes that fit on the current detector. The evaluation of pain reduction will be the primary endpoint, while examining the potential of increased tissue capture without a compromise in image quality will be assessed as secondary endpoints. The enrollment will be consecutive for subjects who sign informed consent to participate. Women participating in the study will present for a screening or diagnostic imaging exam.

All women participating in this study will undergo imaging with the standard and the investigational paddles in a randomized order. This is so that neither the standard paddle nor the investigational curved paddle always have a set order. The intent to randomize is to reduce any bias for either paddle; in that if one is always first the second compression may be more painful, because the woman has been under compression for a number of minutes before having the second set of compressions taken.

Each patient who agrees to participate and is consented and is undergoing a routine screening mammogram will receive 4 view 2D plus 3D combination imaging (LCC, LMO, RCC, RMLO) mammogram, with the current standard paddle. In addition she will also receive a cranio-caudal (CC) and a mediolateral oblique (MLO) in one of her breasts as determined by a randomization scheme with the investigational curved paddle. The amount of compression applied to both mammograms will be that to achieve tautness.

Patients who agree to participate, are consented and are undergoing a diagnostic exam will have diagnostic 2D plus 3D combination imaging as well as a CC or MLO with both the standard paddle and the investigational curved paddle compressed to tautness on the breast of interest. The order of the paddles will be randomized and the view (CC or MLO) will be based in the visibility of the area of interest for which the diagnostic imaging was ordered. (It is possible that one of the views is superior to assess the area of interest).

650 women who are at least 40 years of age will be enrolled. Data will be recorded for compression related parameters such as compression force, thickness, and comfort for both conventional and investigational paddle designs. A standardized 10 point pain scale will be used to record comfort. The investigational paddle that will be tested has been constructed with the natural shape of the breast in mind, rather than current paddles which are straight and flat to try to flatten the breast. In order to obtain the necessary information related to the images, radiologists will be asked to evaluate overall image quality between the standard of care paddle and the investigational paddle.

Each subject will be instructed on the use of the pain scale. The investigational imaging using the Curved Paddle (C-paddle) will be conducted on one breast in either the screening or the diagnostic study population for this study.

At the time of enrollment all screening subjects must be at least 40 years of age and all diagnostic patients must be at least 25 years of age, and be scheduled to have a mammogram as part of their routine clinical care. All subjects will be required to sign an informed consent form prior to enrollment and undergoing imaging with the investigational paddle in the study. All exams will be conducted on the same day. At the

conclusion of the procedure each subject will be asked a few questions related to her overall experience during the visit and her preference for which paddle she preferred.

### **9.1. Subject Inclusion/Exclusion Criteria:**

Inclusion criteria for all subjects are as follows:

#### **Inclusion Criteria**

- Subject is female (born XX) of any race and ethnicity
- Screening Subjects are  $\geq 40$  years old and diagnostic subjects are  $\geq 25$  years old
- Subject will have had a combination 2D plus 3D exam
- If Subject is having a diagnostic workup she has had a 2D plus 3D imaging exam within the last 60 days
- Subject is either having a screening mammogram or presenting for a diagnostic imaging evaluation

#### **Exclusion Criteria**

- Subject is unable or unwilling to undergo informed consent
- Subject is pregnant
- Subject is breast-feeding
- Subject is unable to be imaged on a standard detector; breasts are too large

## **10. DETAILED STUDY PROCEDURE**

A study flow chart is shown below. The study will include 650 subjects. After determining eligibility and informed consent is obtained, the subjects presenting for screening will undergo (2D plus 3D) with the current paddle and 2 views of one breast with the curved paddle (CC and MLO in 2D plus 3D).

[figure not shown]
If the patient is undergoing diagnostic imaging she will have her prescribed diagnostic views followed by a combination (2D plus 3D) CC or MLO with both the standard paddle and the investigational curved paddle compressed to tautness on the breast of interest.

In both the screening and the diagnostic populations, the paddle order will alternate so that for the first subject the order would be standard of care, followed by the investigational paddle. The next subject would have the investigational first followed by the standard of care. The order is changed to prevent distortion in the recorded pain scores since women may find the first compression more or less painful than subsequent compressions.

Both sets of compression on the curved paddle and the standard of care paddle will be to tautness. The force will not be matched exactly since the curved compression paddle may allow imaging of more breast

tissue and forcing the compression level to match the standard of care may result in unnecessary pain to achieve tautness. The technologist will strive to achieve a similar compression without causing excess pain.

[figure not shown]
**Figure 4:** Flowchart showing the enrollment and imaging process

The technical factors such as kilovoltage, tube current and filtration will be determined using AEC (automatic exposure control) in the same manner as conventional 3D exams.

At the completion of each compression for each view and each paddle (the standard procedure and the investigational procedure(s)) each patient will be asked to rate her pain on a 0-10 pain scale. The result will be pain scores for the breast being compressed with both paddles. Additionally, each patient will be asked to point out any specific areas of discomfort on a breast diagram that is experienced during the course of the compression procedures.

**Figure 5:** Pain score used for comfort evaluation

The investigational images will not be used to recommend biopsy and will not be used to cancel work-up or biopsy of any index lesion of concern that was recommended based on the standard of care (SOC) mammograms. However, the investigational images may characterize the index lesion of concern as more suspicious than standard diagnostic imaging and further standard work-up (including targeted extra views, sonography or MRI) may be recommended. The subject and the subject's doctor will be informed of any new finding(s). The subject is not required to undergo further testing.

The investigational images may also allow detection of a new suspicious finding and further standard work-up (including targeted extra views, sonography or MRI) may be recommended. The subject and the subject's doctor will be informed of any new finding(s). The subject is not required to undergo further testing.

If a patient is recalled based on her standard of care imaging, her follow-up procedures will be outside of this study and be conducted as per institutional policy for patient care.

The study technologist conducting the study imaging will then complete a series of questions regarding their experience with the procedures for both paddles using a 5 point Likert scale to compare the investigational procedures against the Standard of Care procedures for areas including but not limited to:

- Overall Ease in positioning for each view on each paddle
- Ability to maintain positioning
- Ability to get high into the Axilla
- Ability to get further back on the chest wall
- Ability to pull in more tissue
- Ability to decrease skin folds
- Ability to decrease neck pulling
- Ability to decrease breast sagging
- Ability to hold the breast in the optimal MLO position

After the images have been acquired a study radiologist will conduct a side by side image comparison of the standard of care images to the investigational images using a 5-point Likert scale to assess the images for:

- Overall Image quality
- Lesion Visibility
- Tissue separation of structures
- Patient Motion

The radiologist will also assess breast density separately on the standard of care and on the investigational images.

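### Section 9 says paddle order is randomized to reduce bias, but Section 10 has sites alternate it, so the order is predictable and not random

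*Combined protocol and SAP*

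**What the plan says.** Section 9 (Study Design) makes the statement for the whole study: "All women participating in this study will undergo imaging with the standard and the investigational paddles in a randomized order". It gives the purpose, "The intent to randomize is to reduce any bias for either paddle", and explains that if one paddle always came first, the second compression might hurt more. For diagnostic women it repeats: "The order of the paddles will be randomized".

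Section 10 (Detailed Study Procedure) covers both the screening and the diagnostic populations and prescribes something else: "the paddle order will alternate so that for the first subject the order would be standard of care, followed by the investigational paddle". It continues: "The next subject would have the investigational first followed by the standard of care". The reason given is again to keep order from distorting the pain scores.

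The one randomization scheme mentioned concerns a different item. In screening women the curved-paddle views are taken "in one of her breasts as determined by a randomization scheme". That decides breast side, not paddle order. On recruitment, Section 9 says "The enrollment will be consecutive for subjects who sign informed consent to participate".

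The Protocol Revision - Summary of Changes does not mention allocation, so neither statement is superseded.

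**The concern.** A fixed starting order with a fixed rule for the next subject contains no random element. The protection that Section 9 promises is therefore not what a site following Section 10 would deliver. The two sections also allow one site to randomize and another to alternate, each believing it complies.

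What alternation lacks is unpredictability. Staff who know the previous order know the next one before deciding whom to approach, or when. Section 21 leaves the approach to the discretion of the radiologist or authorized staff, and eligibility is determined before consent. Consecutive enrollment limits this only in part, because it applies to women who have already signed. Section 10 does not say whether the alternating list runs study-wide, per site or per population, so who could know the next order cannot be settled from the text.

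At stake are some risk of selection into sequences, and the accuracy of any report that paddle order was randomized.

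**Working it through.** The contradiction is one of text. Section 9 says the order is random; Section 10 gives a rule under which each order follows from the one before. The protocol has no figure to reproduce, since Section 11 states that no formal power calculation was done. The arithmetic below only sizes the consequences.

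**Inputs from the documents:** 650 women; up to 5 sites; 2 populations; a 0-10 pain scale; each woman as her own control; paired t-test and ANOVA with no order term named (Section 7.1).

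**Assumed inputs:** order effects, degree of steering, SD of paired differences, and 10 equal strata of 65.

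**1. Constant order effect.** Let D be the curved minus the standard score, and o the extra pain at the second compression. The expected D is the paddle effect plus o when standard comes first, and the paddle effect minus o when curved comes first. The mean of D is therefore shifted by o × (n standard-first − n curved-first) / 650.

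- One alternating list splits 325/325, so the shift is 0.
- Ten separate lists (5 sites × 2 populations), each starting with standard of care, can be off by at most 10 women. With o = 1.0 the shift is 10/650 = 0.015 points.

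Alternation handles this well, however different the women are in general pain level, because that level cancels within each woman.

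**2. Selection into sequences.** Suppose some women are sensitive to order, with order effect oH, and the rest have oL. Let p1 and p2 be the shares of sensitive women in the standard-first and curved-first sequences. With equal sequence sizes:

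bias = (oH − oL) × (p1 − p2) / 2

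| Gap oH − oL (points) | 60% vs 40% | 70% vs 30% |
|---|---|---|
| 0 | 0 | 0 |
| 0.4 | 0.4 × 0.2 / 2 = 0.04 | 0.4 × 0.4 / 2 = 0.08 |
| 0.8 | 0.8 × 0.2 / 2 = 0.08 | 0.8 × 0.4 / 2 = 0.16 |
| 1.2 | 1.2 × 0.2 / 2 = 0.12 | 1.2 × 0.4 / 2 = 0.24 |

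A simulation (4,000 trials of 650 women, SD 2, no true paddle effect, Monte Carlo SE 0.001) agrees. A gap of 0.8 gave 0.079 at 60/40, 0.161 at 70/30 and 0.002 with no steering. A gap of 0 at 70/30 gave 0.003.

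**3. Scale.** The difference detectable with 80% power (two-sided 5%) is (1.96 + 0.84) × SD / √650. This is 0.165, 0.22 and 0.33 points for SDs of 1.5, 2 and 3.

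**4. Predictability.** Under alternation, someone who knows the past orders is right 100% of the time. For a permuted block of size 2n with known boundaries, the best guesser expects n + (4ⁿ / C(2n, n) − 1) / 2 correct guesses:

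- Block of 4: 2 + (16/6 − 1)/2 = 2.833, or 70.8%.
- Block of 6: 3 + (64/20 − 1)/2 = 4.1, or 68.3%.
- Equal mix of 4 and 6: (2.833 + 4.1)/10 = 69.3%.

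**5. Balance lost with blocks.** With blocks of 4 and 6 in 10 strata of 65, 5,000 simulated runs gave a mean imbalance of 2.6 women (95th percentile 6). The maximum is 10 × 3 = 30. For a constant order effect of 1.0 point, the shift is 2.6/650 = 0.004 on average and 30/650 = 0.046 at most.

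**The case against.** The strongest reply is that the bias the protocol names is the order effect itself: the second compression may hurt more, so neither paddle should always come first. Alternation meets that aim, and for a constant order effect it balances slightly better than blocks do. On this reading the word randomized is wrong but the purpose is largely served. This stands, and it limits the weight of the point.

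Second, the remaining bias needs a chain. Staff must know the next order, act on it, and steer women whose order effect differs. A general tendency to report more pain is not enough. Nothing in the documents suggests staff could recognise such women before any compression. Women come for scheduled routine imaging and complete all exams the same day, which narrows timing as a route. Of the six nonzero results above, only 0.24 exceeds the smallest detectable difference of 0.17. This also stands: the figures show what could happen, not what is expected. It does not remove discretion over whom to approach.

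Third, the contradiction could be resolved by calling the method alternation and dropping the claim of randomization. That would make the text truthful, but it gives up the protection Section 9 promises when keeping it costs little.

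Fourth, the flowchart (Figure 4) is not visible in the available text, so any ordering detail there could not be checked. The two sections conflict in any case.

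**Conclusion.** The concern holds. Sections 9 and 10 give incompatible accounts of how paddle order is set, and the operational one is deterministic. A study run under Section 10 could not accurately report its order as randomized.

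The effect on the primary comparison is uncertain and probably modest. It is zero if order effects are the same in all women or if no steering occurs, and 0.04 to 0.24 points under the assumed gaps and splits. Those inputs are illustrative, and the SD range used for scale is also assumed. The point should be corrected because it concerns a stated bias control and the correction is cheap. It is not evidence that the pain result would be wrong.

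**What to change.** Replace the alternation paragraph in Section 10 with a computer-generated order list in permuted blocks (for example sizes 4 and 6), stratified by site and by screening or diagnostic population. Reveal each woman's order only after she has signed consent. Make Section 9 say the same. For screening women the list can be combined with the breast-side scheme. Diagnostic women, imaged on the breast of interest, need a new list.

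The cost is one rewritten paragraph, the lists, a step to open the assignment after consent, and a protocol amendment. Section 19.1 requires the IRB approval to cite the protocol revision level and date; any edit reconciling the two sections carries that cost. If enrollment has already begun, which the documents do not say, record the date of the switch and report the two allocation methods separately. No extra women, images or visits are needed, and the loss of order balance is the small one computed above.

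The change removes certain foreknowledge of the order at enrollment. It does not blind the patient or technologist to the paddle, and it does not alter the imbalance in screening of four standard views against two curved views.

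### In screening women, reversing a four-view standard set and a two-view curved set does not give mirror-image orders, so one eighth of any first- or last-compression pain effect stays in the paired difference

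*Combined protocol and SAP*

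**What the plan says.** Section 9 (Study Design) says that each screening woman "will receive 4 view 2D plus 3D combination imaging (LCC, LMO, RCC, RMLO) mammogram, with the current standard paddle". It continues: "In addition she will also receive a cranio-caudal (CC) and a mediolateral oblique (MLO) in one of her breasts as determined by a randomization scheme", taken with the curved paddle. The Key Protocol Terms define combination images as 2D and 3D acquired under one compression, so a screening woman has six compressions.

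Section 10 (Detailed Study Procedure) says that "the paddle order will alternate so that for the first subject the order would be standard of care, followed by the investigational paddle", and that the next subject has the reverse. The reason given is: "The order is changed to prevent distortion in the recorded pain scores since women may find the first compression more or less painful than subsequent" ones. Pain is rated after every view with each paddle, and "The result will be pain scores for the breast being compressed with both paddles".

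Section 9 gives a related reason for varying the order: the second set may hurt more "because the woman has been under compression for a number of minutes before having the second set of compressions taken".

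Section 7.1 compares the scores with a paired t-test and ANOVA. It names no order, sequence or position factor. The documents do not give the sequence of the four standard views or the allocation ratio for the study breast, and the flowchart (Figure 4) is not shown.

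In diagnostic women the prescribed views come first. One view of the breast of interest then follows with each paddle.

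**The concern.** Reversing the order cancels a first-compression effect only if each paddle is equally likely to supply the first compression that enters the comparison. That fails when the sets differ in length and one set includes a breast that is not compared.

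When the curved set goes first, the woman's first compression always enters the curved score. When the standard set goes first, her first compression may be on the other breast, and then it never enters the pair. The last compression has the same asymmetry.

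The primary result is the within-woman pain difference. A residue of the effect that Section 10 sets out to remove would be read as a paddle effect, and enrolling more women would not shrink it.

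**Working it through.** The plan gives no figure for order balance, so there is nothing to reproduce first.

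**Inputs from the documents:** four standard views (two per breast), two curved views of one breast, paddle sets reversed between subjects, pain scored after each view, comparison on the breast imaged with both paddles (Sections 9 and 10); 650 subjects (Section 11).

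**Assumptions:** the standard views run as one block; each order in half of women; study breast 1:1 and independent of which breast is imaged first.

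**Step 1: positions.** Standard first puts standard views at positions 1-4 and curved at 5-6. Curved first puts curved at 1-2 and standard at 3-6. Share of screening women whose compression at each position is of each kind:

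| Position | Curved | Paired standard | Other breast |
|---|---|---|---|
| 1, 2 | 50% | 25% | 25% |
| 3, 4 | 0% | 50% | 50% |
| 5, 6 | 50% | 25% | 25% |

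The shares are the same for left-left-right-right, for right-left-right-left, and averaged over all 24 orders of the four standard views.

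**Step 2: effect d on the session's first compression only.** Take the mean of two views per paddle, curved minus standard.
- Curved first: shift +d/2.
- Standard first: shift -d/2 if the study breast is imaged first, otherwise 0; average -d/4.
- Overall: 1/2 × d/2 + 1/2 × (-d/4) = d/8.

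A last-compression effect also gives d/8. An estimate adjusted for paddle order averages the same two order-specific means, (d/2 - d/4)/2 = d/8, so a bare order term does not remove it.

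**Step 3: what cancels.** The position weights in the mean difference are +1/8, +1/8, -1/4, -1/4, +1/8, +1/8, a contrast of ends against middle.
- Linear drift: mean position is (1.5 + 5.5)/2 = 3.5 for curved and 1.5/4 + 3.5/2 + 5.5/4 = 3.5 for paired standard. It cancels.
- Second set more painful by s: +s with standard first, -s with curved first. It cancels.
- Each breast's own first compression: +d/2 and -d/2. It cancels.

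**Step 4: unequal breast split.** Let q be the probability that the study breast is the one imaged first, with left-left-right-right order. The first-compression bias is (0.5 - q/2)/2 × d = (1 - q)d/4, and the last-compression bias is q × d/4. Each runs from 0 to d/4 as q varies; at q = 0.5 each is d/8. First and last positions together stay at 2:1 for any q.

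**Step 5: size.** The documents give no d, SD or screening share f. Take d = 1, an assumed SD of the paired difference of 2, and n = 650, so SE = 2/√650 = 0.078. Pooled bias = f × 0.125:

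| f | Bias (points) | Bias/SE |
|---|---|---|
| 0.25 | 0.031 | 0.4 |
| 0.50 | 0.063 | 0.8 |
| 0.75 | 0.094 | 1.2 |
| 1.00 | 0.125 | 1.6 |

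At f = 0.5, an SD of 1.5 gives 0.0625/0.0588 = 1.1 SE and an SD of 2.5 gives 0.0625/0.0981 = 0.6 SE.

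**Step 6: check of the remedy.** With the study-breast views as one block and the other breast always last, positions 1-4 are 50% curved and 50% paired standard. With the other breast always first, the same holds for positions 3-6. The bias is 0 either way.

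**The case against.** The strongest reply is that the sequence is inferred. Nothing in the text fixes the order of the four standard views or says that the other breast's views stay inside the reversed set, and the flowchart that might show it is missing. This stands as a condition on the result. The block reading is still the plain one: Section 10 reverses the paddles as wholes, and Section 9 speaks of a second set of compressions.

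A second reply is that the order effect described in Section 9, a more painful second set, is fully balanced. That is correct. One could also read the first compression in Section 10 as the first paddle's set, and then the reversal works. But Section 10 contrasts it with subsequent compressions in the plural and has pain scored after each one, so the single-compression reading is at least as natural.

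Third, the ANOVA in Section 7.1 could carry a position term. It could, because positions 1-2 and 5-6 each contain both paddles. None is named, however.

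Fourth, Section 11 calls the trial descriptive. That does not dispose of the point: Section 5 states a directional hypothesis, Section 7.1 names a test, and a biased mean is also biased as a description.

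A reader might go further and infer that the reversal fails against order effects in general, that the 2:1 ratio is a stated fact, or that the bias reaches 3.2 SE. The documents support none of these. Several order effects cancel; the ratio rests on an unstated 1:1 split; and 3.2 SE needs all 650 women to be screening subjects and the first two compressions, not just the first, to differ by a full point.

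**Conclusion.** The point holds for screening women and for effects confined to the first or last compression of the session. Under block sequencing and 1:1 breast allocation, one eighth of such an effect remains in their mean paired difference: 0.125 points for a one-point effect, or about 0.06 points (0.8 SE at an assumed SD of 2 and n = 650) if half the sample is screening.

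The direction cannot be given, since Section 10 allows the first compression to be more or less painful. A more painful first or last compression counts against the curved paddle and a less painful one favours it; opposite effects at the two ends would offset. It would therefore be wrong to infer that the design favours the curved paddle. The diagnostic comparison is unaffected.

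This is a modest flaw and does not invalidate the design. It is worth correcting because it leaves open the distortion that Section 10 says is prevented, and because correction is cheap.

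**What to change.** In Sections 9 and 10 (and Figure 4 if it shows the sequence), for screening women: take the study breast's CC and MLO with the first paddle, then the same views in the same order with the second paddle, as one block. Place the other breast's two standard views always before, or always after, that block. State the study-breast allocation ratio.

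The number of images and the dose do not change. The cost is one extra paddle swap, and a standard exam split around the curved views, in about half of screening women. If enrolment has already begun, which the documents do not say, analyse women imaged under the two sequences as separate strata.

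If the sequence cannot be changed, record the position of every compression and include a compression-position term in the ANOVA of Section 7.1. An order term alone is not enough. This fallback costs precision. With left-left-right-right order, equal cells, paired scores only and free effects for the three position pairs, the four cells have expected differences t + a, t + a - b, t - b and t - a, where t is the paddle effect and a and b are the effects of positions 5-6 and 3-4 relative to 1-2. Least squares then estimates t by averaging the first and last cells, so its variance is 1/2 of a cell variance against 1/4 for the plain mean of all four. Re-sequencing is therefore the better choice.
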